#### 10.5.2.1. Handling of Missing Dates

Element	Reporting Detail
General	Partial dates will be displayed as captured in subject listing displays.
Adverse Events	
 
• The eCRF allows for the possibility of partial dates (i.e., only month and year) to be recorded for AE start and end dates; that is, the day of the month may be missing. In such a case, the following conventions will be applied for calculating the time to onset and the duration of the event: 
 
○ Missing Start Day: First of the month will be used unless this is before the start date of study treatment; in this case the study treatment start date will be used and hence the event is considered On-treatment as per Appendix 2: Treatment States and Phases.
 
○ Missing Stop Day: Last day of the month will be used, unless this is after the stop date of study treatment; in this case the study treatment stop date will be used.
 
 
 
• Completely missing start or end dates will remain missing, with no imputation applied. Consequently, time to onset and duration of such events will be missing.
 

Element	Reporting Detail
	
 
• Start or end dates which are completely missing (i.e. no year specified) will remain missing, with no imputation applied.
 

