	
administered as a single IV infusion on Day 1.
 
In Part 3, subjects will remain confined to the clinical unit from admission on Day -1 until all scheduled safety and PK assessments have been completed on Day 3. The duration of study (from Screening to the Follow-up visit) for each subject will be up to approximately 43 days.

Dosing	
 
For Part 1, doses are planned to escalate in a sequential fashion contingent on the safety, tolerability, and PK profile of approximately 4 subjects who received active treatment in the previous cohort. The evaluated subjects should be followed for a minimum of 48 hours after dosing. Dose escalations or reductions will progress with modifications based on the preliminary safety, tolerability, and PK data from the preceding cohorts.
 
For Part 2, doses are planned to escalate in a sequential fashion based on the preliminary safety, tolerability, and PK data from Part 1 and at least 14 days of repeat dosing in approximately 5 subjects who received active treatment in the previous cohort in Part 2. The evaluated subjects should be followed for a minimum of 24 hours after dosing on Day 15. The dosing frequency, duration of dosing, and decision to dose in the next dose level may be changed based on the safety, tolerability, or PK findings in Part 1 or earlier doses in Part 2.
 
The dose in Part 3 will be administered as a single IV infusion on Day 1.
 

Treatment Assignment	
 
For Part 1 on Day 1, before study drug administration, subjects will be randomized to treatment with either GSK3342830 or placebo in a 3:1 ratio. As a safety precaution, all Part 1 cohorts will be split into 2 sub-cohorts for sentinel dosing. In each cohort, the first 2 subjects will receive either GSK3342830 or placebo (1 active/1 placebo). Dosing in the remaining 6 subjects (5 active/1 placebo) in that cohort will occur at least 24 hours later based on the safety results from the first sub-cohort.
 
For Part 2 on Day 1, before study drug administration, subjects will be randomized to treatment with either GSK3342830 or placebo in a 4:1 ratio.
 
For Part 3 on Day 1, before study drug administration, subjects will be randomized to treatment with either GSK3342830 or placebo in a 4:1 ratio.
 

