**Time and Events Table: Part 1 - Single Dose Escalation and Part 3 – Single Dose**

Procedure	Day 1																Day 2	Day 3		
	Hours relative to treatment administration																			
	Pre-dose	0	0.5	1	1.25	1.5	2	3	3.5	4	4.5	5	6	8	10	12	16	24	36	48
Randomization	X																			
12-lead ECG 	X		X	X		X	X	X		X			X			X		X		X
Vital signs (BP, HR, oral temperature, respiration rate)	X		X	X		X	X	X		X			X			X		X		X
Fasting clinical chemistry, hematology, and urinalysis 																		X		
Treatment administration 		X																		
Blood collection for pharmacokinetics 	X		X	X	X	X	X	X	X	X	X	X	X	X	X	X	X	X	X	X
Urine collection for pharmacokinetics 	X	X								X				X		X		X		X
Continuous cardiac monitoring 	X	-----Continuous review----->																		
AE review		X	-----Continuous review----->																	
SAE review	X	-----Continuous review----->																		
Concomitant medication review	X	-----Continuous review----->																		
Discharge from inpatient unit 																				X

AE = adverse event, BP = blood pressure, ECG = electrocardiogram, HR = heart rate, SAE = serious adverse event.

NOTES:

1. Triplicate 12-lead ECGs to be obtained at least 5 minutes apart within 1 hour before dosing. Single ECGs will be obtained at all other time points.
2. An aliquot of the urine sample will be collected for neutrophil gelatinase-associated lipocalin (NGAL) and kidney injury molecule 1 (KIM-1). These samples may be analyzed after the end of the study if a clinical signal is detected. Instructions for collection and storage of these urine samples are included in the Study Reference Manual. The albumin to creatinine ratio will be determined using the first morning void urine on Day 2.
3. GSK3342830 or placebo will be administered as a single IV infusion in the morning on Day 1. The planned infusion duration time is 1 hour.
4. Pharmacokinetic blood samples will be collected for GSK3342830 and potential metabolites. At the end of the study the saved blood samples from a predicted therapeutically-relevant dose level and higher dose level for plasma PK analysis of parent and the highest dose level completed for metabolite profile, will be transferred to a GSK specified laboratory. Details of PK sample collection and storage will be provided in the Study Reference Manual.

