4. GSK3342830 or placebo will be administered as a single IV infusion in the morning on Day 1, TID IV infusions (approximately every 8 hours) on Days 2, 3, 4, 5, 6, 7, 8, 9, 10, 11, 12, 13, and 14, and as a single IV infusion in the morning on Day 15. The planned infusion duration time is 1 hour.

Footnotes are continued on the next page.

5. Pharmacokinetic samples for GSK3342830 and potential metabolites will be collected on Day 1 at the following time points: pre-dose (within 15 minutes before dosing) and 0.5, 1 (end of infusion), 1.25, 1.5, 2, 2.5, 3, 3.5, 4, 4.5, 5, 6, 8, 10, 12, 16, and 24 hours after the start of infusion. Single pre-dose trough samples will be taken on the mornings of Days 3, 6, 9, 12, and 13. Serial samples will be collected on Day 15 at the following time points: pre-dose (within 15 minutes before dosing) and 0.5, 1 (end of infusion), 1.25, 1.5, 2, 2.5, 3, 3.5, 4, 4.5, 5, 6, and 8 hours after the start of infusion. At the end of the study, the saved blood samples from a predicted therapeutically-relevant dose level and higher dose level for plasma PK analysis of parent and from the highest dose level completed for potential metabolite profile will be transferred to a GSK specified laboratory. Details of PK sample collection and storage will be provided in the Study Reference Manual.
6. Pooled urine samples will be collected on Day 1 and Day 15 over the following time intervals: pre-dose (within a 24-hour period before dosing, may begin on Day -1) and 0 to 8 and 8 to 24 hours post-dose. Two aliquots of urine samples for baseline analysis may be collected from any time after admission to just before dosing on Day 1. At the end of the study, the saved urine samples from a predicted therapeutically-relevant dose level and higher dose level for urinary PK analysis of parent and from the highest dose-level completed for potential metabolite profile, will be transferred to a GSK specified laboratory. Urine will be collected in opaque bottles to maintain blind of blinded study site personnel. Details of urine sample collection and storage will be provided in the Study Reference Manual.
7. Continuous dual-lead telemetry will be initiated on Day -1 at least 8 hours before treatment administration on Day 1 and will continue until 48 hours post dose.
8. Subjects will be discharged from the clinical unit after the Day 16 assessments are complete.

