#### 10.2.2.2. Treatment States for AE Data

Treatment State	Definition
Pre-Treatment	AE Start Date/time < Study Treatment Start Date/time
On-Treatment	If AE onset date/time is on or after treatment start date & on or before treatment stop date/time. Study Treatment Start Date/time ≤ AE Start Date/time ≤ Study Treatment Stop Date/time + 2 days
Post-Treatment	If AE onset date/time is after the treatment stop date/time. AE Start Date/time > Study Treatment Stop Date/time + 2 days
Onset Time Since 1 st Dose (Days)	If Treatment Start Date/time > AE Onset Date/time, = AE Onset Date - Treatment Start Date If Treatment Start Date/time ≤ AE Onset Date/time, = AE Onset Date - Treatment Start Date + 1 Missing otherwise.
Duration (Days)	AE Resolution Date – AE Onset Date + 1
Drug-related	If relationship is marked 'YES' on CRF OR value is missing.

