**10.5.2.2. Handling of Partial Dates**

Element	Reporting Detail
Concomitant Medications	
 
• Partial dates for any concomitant medications recorded in the CRF will be imputed using the following convention:                             
 
○ If the partial date is a start date, a '01' will be used for the day and 'Jan' will be used for the month
 
○ If the partial date is a stop date, a '28/29/30/31' will be used for the day (dependent on the month and year) and 'Dec' will be used for the month.
 
 
 
• The recorded partial date will be displayed in listings.
 

Adverse Events	
 
• Any partial dates for adverse events will be raised to data management. If the full date cannot be ascertained, the following assumptions will be made:                             
 
○ If the partial date is a start date, a '01' will be used for the day and 'Jan' will be used for the month.
 
○ However, if these results in a date prior to Week 1 Day 1 and the event could possibly have occurred during treatment from the partial information, then the Week 1 Day 1 date will be assumed to be the start date.
 
○ The AE will then be considered to start on-treatment (worst case).
 
○ If the partial date is a stop date, a '28/29/30/31' will be used for the day (dependent on the month and year) and 'Dec' will be used for the month.
 
 
 
• The recorded partial date will be displayed in listings.
 

----------------	---

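### The SAP cuts a missing AE stop day back to the last dose, so events starting after that dose get a listed duration of zero or less, and a second section gives a different rule

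*SAP*

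**What the plan says.** SAP 10.5.2.1 deals with adverse events recorded with month and year but no day. Its conventions are "for calculating the time to onset and the duration of the event". A missing stop day becomes the last day of the month, "unless this is after the stop date of study treatment; in this case the study treatment stop date will be used".

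SAP 10.2.2.2 defines duration in days as "AE Resolution Date – AE Onset Date + 1".

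The dosing schedule fixes the treatment stop date. For Parts 1 and 3 the time and events table says "GSK3342830 or placebo will be administered as a single IV infusion in the morning on Day 1", and SAP 2.3 says of Part 3: "The dose in Part 3 will be administered as a single IV infusion on Day 1". In Part 2 the last dose is given "and as a single IV infusion in the morning on Day 15".

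SAP 10.5.2.2 then gives rules for partial AE dates a second time. Such dates go first to data management. If the full date cannot be found, a partial stop date takes the last day of the month, which "will be used for the day (dependent on the month and year"), and December for the month. This section has no cap at treatment stop. Neither section refers to the other.

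**The concern.** In a single-dose part the cap is the dosing day itself. A recorded stop month normally ends after Day 1, so the cap nearly always applies and the event is ended on Day 1 even if it began later. The plan expects later onsets. AEs are collected to the follow-up contact, 7 to 10 days after the last dose, and SAP 10.2.2.2 counts an event as on-treatment if it starts within 2 days of treatment stop. An on-treatment event on Day 2 or 3 after a single dose could therefore be listed with a duration of 0 or -1.

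Two programmers following different sections could also give the same event different durations. At stake are impossible or conflicting values in the AE and SAE listings of a first-in-human study whose primary endpoint is safety.

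**Working it through.** The documents state no figure for this point, so there is nothing to reproduce. The check applies the SAP's own rules.

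**Inputs**
- Last dosing day L: Day 1 in Parts 1 and 3, Day 15 in Part 2 for a subject who completes dosing (SAP time and events tables).
- Latest onset collected: the follow-up visit, 7 to 10 days after the last dose. That is Day 8 to 11 in Parts 1 and 3 (1 + 7 to 1 + 10) and Day 22 to 25 in Part 2 (15 + 7 to 15 + 10).
- Imputed stop (SAP 10.5.2.1): the earlier of month-end and treatment stop.
- Duration (SAP 10.2.2.2): stop - onset + 1.

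**Formula.** When the cap applies, the stop is Day L. For onset on Day d, duration = L - d + 1. This is zero or less whenever d is greater than L.

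| Parts 1 and 3: onset day | 1 - d + 1 | Part 2: onset day | 15 - d + 1 |
|---|---|---|---|
| 1 | 1 | 15 | 1 |
| 2 | 0 | 16 | 0 |
| 3 | -1 | 17 | -1 |
| 8 | -6 | 22 | -6 |
| 11 | -9 | 25 | -9 |

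**How often the cap applies in Parts 1 and 3.** Take every dosing date in one calendar year (2016, 366 dates), onset on Days 1 to 11 and true durations of 1 to 5 days. The year and the durations are illustrative. That makes 366 x 11 x 5 = 20,130 combinations.
- The cap applied in 20,118 of them (99.9%). The other 12 have the dose on the last day of a month and the event ending that same day, where month-end is Day 1 anyway.
- All 366 x 10 x 5 = 18,300 combinations with onset after Day 1 gave a duration of zero or less.
- All 366 x 5 = 1,830 combinations with onset on Day 1 gave exactly 1 day, whatever the true duration.

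**The two sections compared.** Suppose a dose on 6 June and onset on Day 3 (8 June), with June recorded as the stop month.
- SAP 10.5.2.1: stop 6 June, duration 6 - 8 + 1 = -1.
- SAP 10.5.2.2, keeping the recorded month: stop 30 June, duration 30 - 8 + 1 = 23.
- SAP 10.5.2.2, with December applied literally: stop 31 December, duration 23 + 31 + 31 + 30 + 31 + 30 + 31 = 207.

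**Where duration appears.** The shells of Listing 12 (all AEs) and Listing 14 (SAEs) have a duration field, and Listing 13 (drug-related AEs) reuses the Listing 12 shell. The AE tables, 2.1 to 2.5, do not use duration.

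**The case against.** The strongest reply is that the effect is small and may never occur.

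- SAP 10.5.2.2 sends partial AE dates to data management before any imputation. Subjects are confined for 48 hours after dosing in Parts 1 and 3 and to Day 16 in Part 2, with continuous AE review. Few stop days, perhaps none, should stay missing. This stands.
- Both sections show the partial date as recorded in the listings, so a reader would see month and year beside the odd duration. This makes the error easier to spot but does not make the value right.
- The two sections may be meant for different cases: 10.5.2.1 for a missing day, 10.5.2.2 for a missing day and month. That is a fair reading, and it is why overlapping scope describes the problem better than flat contradiction. But the SAP does not say so, and making the imputed day depend on the month implies that the month may be known.

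A reader might infer three stronger things, none of which the documents support. The first is that the rule distorts the primary safety results. Protocol 9.4.1 summarises AEs by number, percentage, severity and relationship, and by class and term, not by duration. Incidence and on-treatment status depend on the start date. The second is that missing stop days cluster in long events continuing after discharge. That is plausible, but nothing in the documents shows it, and the defect does not need it. The third is that every affected event gets an impossible duration. A Day 1 onset in Parts 1 and 3 gets 1 day, and onsets on Days 1 to 15 in Part 2 stay positive for subjects who complete dosing. Those values may be too short, but they are not impossible.

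**Conclusion.** The rule is wrong as written. Followed exactly, SAP 10.5.2.1 gives a duration of zero or less to any event that starts after the last dosing day and whose stop day stays missing after query: down to -9 for onset at the latest follow-up day in each part. It also sets every such Day 1 event in Parts 1 and 3 to 1 day. Because SAP 10.5.2.2 overlaps it without a cap and no precedence is stated, the same event can get different answers.

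The effect is confined to the duration field in AE Listings 12 to 14, as their shells are written. The documents give no basis for estimating how many events would be affected.

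The arithmetic assumes that treatment stop is the last scheduled dosing day. A Part 2 subject who stops early has an earlier cap, and the fault then starts at an earlier onset day. The 6 June date and the 2016 calendar are illustrations only. The formula L - d + 1 does not depend on them.

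**What to change.** In SAP 10.5.2.1, remove the cap at treatment stop. Set a missing stop day to the last day of the recorded month, and never to a date before onset. If an upper limit is wanted, use the subject's last-contact or last AE follow-up date. The Follow-up visit is not a safe limit where an event is followed beyond it: Protocol 7.3.1.3 follows SAEs and AEs of special interest until they resolve or stabilise, so a limit there would again cut off events known to have lasted longer.

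In SAP 10.5.2.2, keep the query to data management, and restrict the December rule to stop dates whose month is also missing. The stop rule there should not simply be deleted. SAP 10.5.2.1 covers only a missing day or a wholly missing date, so a stop date recorded by year alone would be left without a rule. One rule then applies to each type of partial date.

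The cost is a wording change in two adjacent SAP sections and a small change to one derivation. No data collection, table or analysis changes.

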**10.5.2.2. Handling of Partial Dates**

Element	Reporting Detail
Concomitant Medications	
 
• Partial dates for any concomitant medications recorded in the CRF will be imputed using the following convention:                             
 
○ If the partial date is a start date, a '01' will be used for the day and 'Jan' will be used for the month
 
○ If the partial date is a stop date, a '28/29/30/31' will be used for the day (dependent on the month and year) and 'Dec' will be used for the month.
 
 
 
• The recorded partial date will be displayed in listings.
 

Adverse Events	
 
• Any partial dates for adverse events will be raised to data management. If the full date cannot be ascertained, the following assumptions will be made:                             
 
○ If the partial date is a start date, a '01' will be used for the day and 'Jan' will be used for the month.
 
○ However, if these results in a date prior to Week 1 Day 1 and the event could possibly have occurred during treatment from the partial information, then the Week 1 Day 1 date will be assumed to be the start date.
 
○ The AE will then be considered to start on-treatment (worst case).
 
○ If the partial date is a stop date, a '28/29/30/31' will be used for the day (dependent on the month and year) and 'Dec' will be used for the month.
 
 
 
• The recorded partial date will be displayed in listings.
 

----------------	---

## 10.6. Appendix 6: Values of Potential Clinical Importance

### 10.6.1. ECG

ECG Parameter	Units	Potential Clinical Importance Range	
		Lower	Upper
Absolute			
Absolute QTc Interval	msec	> 450 	
		> 450 	≤ 479 
		≥ 480 	≤ 499 
		≥ 500 	
Absolute PR Interval	msec	< 110 	> 220 
Absolute QRS Interval	msec	< 75 	> 110 
Change from Baseline			
Increase from Baseline QTc	msec	≤ 30 	
	msec	> 30 	≤ 59 
	msec	≥ 60 	

**NOTES:**

1. Represent standard ECG values of PCI for HV studies.
2. Represent further subdivisions of ECG values for analysis.

### 10.6.2. Vital Signs

Vital Sign Parameter (Absolute)	Units	Potential Clinical Importance Range	
		Lower	Upper
Systolic Blood Pressure	mmHg	< 85	> 160
Diastolic Blood Pressure	mmHg	< 45	> 100
Heart Rate	bpm	< 40	> 110

## 10.7. Appendix 7: DMID Adult Toxicity Tables for Adverse Event Assessment

### 10.7.1. Laboratory Values

Parameter values are converted to use SI units.

#### HEMATOLOGY

	Grade 1	Grade 2	Grade 3	Grade 4
Hemoglobin	95 to 105 G/L	80 to 94 G/L	65 to 79 G/L	<65 G/L
Absolute neutrophil count	1.0 to 1.5 10  /L	0.75 to 0.999 10  /L	0.5 to 0.749 10  /L	<0.5 10  /L
Platelets	75 to 99.999 10  /L	50 to 74.999 10  /L	20 to 49.999 10  /L	<20 10  /L
White Blood Cells	11 to 13 10  /L	13 to 15 10  /L	15 to 30 10  /L	>30 or <1 10  /L
% Polymorphonuclear leukocytes + band cells	>80%	90 to 95%	>95%	N/A
Abnormal Fibrinogen	Low: 1 to 2 G/L High: 4 to 6 G/L	Low: <1 G/L High: >6 G/L	Low: <0.5 G/L High: N/A	Fibrinogen associated with gross bleeding or with disseminated coagulation
Fibrin Split Product	0.020 to 0.040 G/L	0.041 to 0.050 G/L	0.051 to 0.060 G/L	>0.060 G/L
Prothrombin Time	1.01 to 1.25 × ULN	1.26 to 1.5 × ULN	1.51 to 3.0 × ULN	>3 × ULN
Activated Partial Thromboplastin	1.01 to 1.66 × ULN	1.67 to 2.33 × ULN	2.34 to 3 × ULN	>3 × ULN
Methemoglobin	5.0 to 9.9%	10.0 to 14.9%	15.0 to 19.9%	>20%

N/A = not applicable; ULN = upper limit of normal.

#### CHEMISTRIES

	Grade 1	Grade 2	Grade 3	Grade 4
Hyponatremia	130 to 135 MMOL/L	123 to 129 MMOL/L	116 to 122 MMOL/L	<116 MMOL/L or abnormal sodium with mental status changes or seizures
Hypernatremia	146 to 150 MMOL/L	151 to 157 MMOL/L	158 to 165 MMOL/L	>165 MMOL/L or abnormal sodium with mental status changes or seizures
Hypokalemia	3.0 to 3.4 MMOL/L	2.5 to 2.9 MMOL/L	2.0 to 2.4 MMOL/L or intensive replacement therapy of hospitalization required	<2.0 MMOL/L or abnormal potassium with paresis, ileus, or life-threatening arrhythmia
Hyperkalemia	5.6 to 6.0 MMOL/L	6.1 to 6.5 MMOL/L	6.6 to 7.0 MMOL/L	>7.0 MMOL/L or abnormal potassium with

				life-threatening arrhythmia
Hypoglycemia	3.0 to 3.55 MMOL/L	2.22 to 2.99 MMOL/L	1.67 to 2.21 MMOL/L	<1.67 MMOL/L or abnormal glucose with mental status changes or coma
Hyperglycemia (nonfasting and no prior diabetes)	6.44 to 8.88 MMOL/L	8.89 to 13.88 MMOL/L	13.89 to 27.75 MMOL/L	>27.76 MMOL/L or abnormal glucose with ketoacidosis or seizures
Hypocalcemia (corrected for albumin)	2.10 to 1.95 MMOL/L	1.94 to 1.75 MMOL/L	1.74 to 1.52 MMOL/L	<1.52 MMOL/L or abnormal calcium with life-threatening arrhythmia or tetany
Hypercalcemia (corrected for albumin)	2.64 to 2.87 MMOL/L	2.88 to 3.12	3.13 to 3.37 MMOL/L	>3.37 MMOL/L or abnormal calcium with life-threatening arrhythmia
Hypomagnesemia	0.7 to 0.6 MMOL/L	0.59 to 0.45 MMOL/L	0.44 to 0.3 MMOL/L	<0.3 MMOL/L or abnormal magnesium with life-threatening arrhythmia
Hypophosphatemia	0.7 to 0.8 MMOL/L	0.5 to 0.6 MMOL/L or replacement Rx required	0.3 to 0.4 MMOL/L intensive therapy or hospitalization required	<0.3 MMOL/L or abnormal phosphate with life-threatening arrhythmia
Hyperbilirubinemia (when accompanied by any increase in other liver function test)	1.1 to <1.25 × ULN	1.25 to <1.5 × ULN	1.5 to 1.75 × ULN	>1.75 × ULN
Hyperbilirubinemia (when other liver function tests are in the normal range)	1.1 to <1.5 × ULN	1.5 to <2.0 × ULN	2.0 to 3.0 × ULN	>3.0 × ULN
Blood urea nitrogen	1.25 to 2.5 × ULN	2.6 to 5 × ULN	5.1 to 10 × ULN	>10 × ULN
Hyperuricemia (uric acid)	446 to 595 UMOL/L	596 to 714 UMOL/L	715 to 892 UMOL/L	>892 UMOL/L
Creatinine	1.1 to 1.5 × ULN	1.6 to 3.0 × ULN	3.1 to 6.0 × ULN	>6 × ULN or dialysis required

Rx = therapy; ULN = upper limit of normal.

ENZYMES				
	Grade 1	Grade 2	Grade 3	Grade 4
Aspartate aminotransferase	1.1 to <2.0 × ULN	2.0 to <3.0 × ULN	3.0 to 8.0 × ULN	>8.0 × ULN
Alanine aminotransferase	1.1 to <2.0 × ULN	2.0 to <3.0 × ULN	3.0 to 8.0 × ULN	>8.0 × ULN
Gamma to glutamyl transferase	1.1 to <2.0 × ULN	2.0 to <3.0 × ULN	3.0 to 8.0 × ULN	>8.0 × ULN
Alkaline Phosphatase	1.1 to <2.0 × ULN	2.0 to <3.0 × ULN	3.0 to 8.0 × ULN	>8.0 × ULN
Amylase	1.1 to 1.5 × ULN	1.6 to 2.0 × ULN	2.1 to 5.0 × ULN	>5.1 × ULN
Lipase	1.1 to 1.5 × ULN	1.6 to 2.0 × ULN	2.1 to 5.0 × ULN	>5.1 × ULN

ULN = upper limit of normal.

URINALYSIS				
	Grade 1	Grade 2	Grade 3	Grade 4
Proteinuria	1+ or 200 MG to 1 GM loss/day	2 to 3+ or 1 to 2 GM loss/day	4+ or 2 to 3.5 GM loss/day	Nephrotic syndrome or >3.5 GM loss/day
Hematuria	Microscopic only <10 RBC/HPF	Gross, no clots >10 RBC/HPF	Gross, with or without clots, or red blood cells casts	Obstructive or required transfusion

HPF = high-powered field; RBC = red blood cells.

